9.3. Reporting of Adverse Events and Serious Adverse Events

9.3.1. Reporting of Adverse Events

Adverse event data will be collected from the time of first dose until 28 days after last dose.

All AEs, whether believed by the Investigator to be related or unrelated to the investigational product, must be documented in the subject's medical records, in accordance with the Investigator's normal clinical practice and on the AE CRF. Each AE is to be evaluated for duration, intensity, frequency, seriousness, outcome, other actions taken, and relationship to the investigational product. Redacted medical record source documents will be requested for all SAEs and emergency room visits.

9.3.2. Reporting of Serious Adverse Events

In agreeing to the provisions of this protocol, the Investigator accepts all responsibilities for immediately reporting SAEs to the Sponsor. Immediate reporting implies within 24 hours of becoming aware of the occurrence of an SAE.

After informed consent for the clinical trial has been obtained but prior to initiation of study drug, only SAEs related to protocol-mandated assessments should be reported.

SAE data will be collected from the time of the first dose until 28 day after the last dose.

The Investigator will assess whether the event is causally related to the investigational product. The Sponsor will also assess whether the event is causally related to the investigational product, in addition to assessing the overall safety profile of the investigational product. If an Investigator becomes aware of an SAE that may be attributable to the investigational product at any time after

^b Examples of self-care activities of daily living include bathing, dressing and undressing, feeding oneself, using the toilet, and taking medications, as performed by subjects who are not bedridden.

^c If an event is assessed as a "significant medical event," it must be reported as a SAE per the definition of SAE.

^d Grade 4 and 5 events must be reported as SAEs per the definition of SAE.

the end of the study, the Sponsor should be notified immediately (ie, within 24 hours) by completing and sending a Serious Adverse Event Report Form.

The Investigator must report SAEs by completing and sending a Serious Adverse Event Report Form and completing the AE/SAE CRF section.

Investigators should record all case details that can be gathered immediately (ie, within 24 hours after learning of the event) on the SAE report form and submit the report via fax or email (please refer to the Study Manual).

The Sponsor or designee will notify the appropriate regulatory authorities in accordance with local government regulations.

Following the initial report, any additional information obtained by the Investigator about the SAE must be reported promptly to the Sponsor in the same manner as described above for the initial SAE report. Redacted medical record source documents will be requested for all SAEs and emergency room visits.

9.3.3. Deaths

Death due to disease progression will not be reportable as an SAE. All deaths, regardless of relationship to study drug, must be recorded on the Death CRF and on the Adverse Event CRF if considered an adverse event.

Death should be considered an outcome and not a distinct event. The event or condition that caused or contributed to the fatal outcome should be recorded as the single medical concept on the Adverse Event CRF. Generally, only one such event should be reported. The term "sudden death" should be used only for the occurrence of an abrupt and unexpected death due to presumed cardiac causes in a subject with or without preexisting heart disease, within 1 hour after the onset of acute symptoms or, in the case of an unwitnessed death, within 24 hours after the subject was last seen alive and stable. If the cause of death is unknown and cannot be ascertained at the time of reporting, "unexplained death" should be recorded on the Adverse Event CRF. If the cause of death later becomes available (eg, after autopsy), "unexplained death" should be replaced by the established cause of death.

9.3.4. Follow-up of Adverse Events and Serious Adverse Events

All AEs must be followed until the AE resolves, is no longer of clinical concern, has stabilized or is otherwise explained, or the subject is lost to follow-up.

AEs ongoing at the final follow-up assessment that are deemed to be "related" to the investigational product or of other clinical significance must be followed for as long as necessary to adequately evaluate the safety of the subject or until the event stabilizes, resolves, or is no longer of clinical concern. If resolved, a resolution date for the AE should be documented in the CRF. The Investigator must ensure that follow-up includes any supplemental investigations indicated to elucidate the nature and/or causality of the AE. This may include additional laboratory tests or investigations, or consultation with other healthcare professionals, as considered clinically appropriate by the Investigator.

9.4. Pregnancy

9.4.1. Exposure During Pregnancy

For investigational products and for marketed products, an exposure during pregnancy occurs if:

- A female becomes, or is found to be, pregnant either while receiving or having been exposed to (eg, because of treatment or environmental exposure) the investigational product; or the female becomes, or is found to be, pregnant after discontinuing and/or being exposed to the investigational product. An example of environmental exposure would be a case involving direct contact with the TPX-0046 product in a pregnant woman (eg, a nurse reports that she is pregnant and has been exposed to chemotherapeutic products).
- A male subject has been exposed (eg, because of treatment or environmental exposure) to the investigational product before or around the time of conception and/or is exposed during his partner's pregnancy.

If a study subject or study subject's partner becomes or is found to be pregnant during the subject's treatment or within after the last dose of the investigational product, for female subjects and male subjects respectively, the Investigator must submit this information to on a Pregnancy Report Form In addition, the Investigator must submit information regarding environmental exposure to a Sponsor product in a pregnant woman (eg, a subject reports that she is pregnant and has been exposed to a cytotoxic product by inhalation or spillage). This must be done regardless of whether an AE has occurred and within 24 hours of awareness of the exposure. The information submitted should include the anticipated date of delivery (see below for information related to termination of pregnancy).

The Investigator will follow the pregnancy until completion or until pregnancy termination and notify the Sponsor's Medical Monitor/or designee of the outcome as a follow-up to the initial pregnancy report. In the case of a live birth, the structural integrity of the neonate can be assessed at the time of birth. In the event of a termination, the reason(s) for the termination should be specified and, if clinically possible, the structural integrity of the terminated fetus should be assessed by gross visual inspection (unless pre-procedure test findings are conclusive for a congenital anomaly and the findings are reported).

If the outcome of the pregnancy meets the criteria for an SAE (ie, ectopic pregnancy, spontaneous abortion, intrauterine fetal demise, neonatal death, or congenital anomaly [in a liveborn baby, a terminated fetus, an intrauterine fetal demise, or a neonatal death]), the Investigator should follow the procedures for reporting SAEs.

Additional information about pregnancy outcomes that are reported as SAEs follows:

- Spontaneous abortion to include miscarriage and missed abortion.
- Neonatal deaths that occur within one month of birth should be reported, without regard to causality, as SAEs. In addition, infant deaths after one month should be reported as SAEs when the Investigator assesses the infant death as related or possibly related to exposure to the investigational product.

Additional information regarding the exposure during pregnancy may be requested by the Investigator. Further follow-up of birth outcomes will be handled on a case-by-case basis (eg,

follow-up on preterm infants to identify developmental delays). In the case of paternal exposure, the Investigator will request consent from the study subject and partner for additional information. The Investigator must document in the source documents that consent was requested.

9.4.2. Pregnancy Reporting

Female subjects or partners of male subjects of childbearing potential will be instructed to immediately inform the Investigator if they become pregnant during the study or within after the last dose of the investigational product, for female subjects and male subjects respectively.

The Investigator should discontinue the investigational product and counsel the subject or partner of a male subject, discussing the risks of the pregnancy and the possible effects on the fetus. Monitoring should continue until conclusion of the pregnancy. Any SAEs associated with the pregnancy (eg, an event in the fetus, an event in the mother during or after the pregnancy, or a congenital anomaly/birth defect in the child) should be reported and submitted within 24 hours.

9.4.3. Birth Defects and Abortions

Any congenital anomaly/birth defect in a child born to a female subject or partner of a male subject exposed to the investigational product should be classified as an SAE and reported as such. Any spontaneous abortion or miscarriage should be reported in the same fashion (therapeutic abortions are excluded from expedited reporting and would be captured as pregnancy outcome information).

For additional guidance regarding use of contraceptives see Appendix B.

10. STATISTICAL METHOD ANALYSIS

Detailed methodology for summary and statistical analyses of the data collected in this trial will be documented in a Statistical Analysis Plan (SAP), which will be maintained by the Sponsor or their designee. The SAP may modify the initial analysis plan outlined in the protocol; however, any major modifications of the primary endpoint and/or analysis methods will also be reflected in a protocol amendment.

10.1. Analysis Sets

10.1.1. Full Analysis Set

The Full Analysis Set (FAS) consists of all subjects who receive at least one full or partial dose of TPX-0046. This will be the same as the Safety Analysis Set. The FAS set will be used for the summary of subject dispositions, demographics, and baseline characteristics, and safety analysis.

10.1.2. Efficacy Evaluable Analysis Set

Efficacy Evaluable (EE) Analysis Set will include all enrolled subjects who (1) have received at least one dose of study treatment; (2) *RET* fusion+ or mutation+ from local testing (LTD) can be confirmed by central lab; (3) have a baseline tumor assessment with measurable disease and have

at least 1 on-study tumor assessment per RECIST v1.1; and (4) have no major protocol violations that could affect efficacy.

The EE analysis set will be used for efficacy analyses for Phase 1.

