10.3.4. Efficacy Analyses

Radiologic assessments evaluated by the Investigator will be explored for Phase I in efficacy analysis set. Number of subjects with ORR will be summarized.

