10.3.4.1. Objective Response Rate

The ORR will be defined as the proportion of subjects with a confirmed complete response (CR) or partial response (PR). A confirmed response is a response that persists on a repeat imaging performed at least 4 weeks after initial documentation of response. Subjects with a confirmed objective response (CR or PR) will be referred to as responders. Non-responders will include subjects without a confirmed objective response, stable disease (SD), progressive disease (PD), not evaluable (NE), or non-CR/non-PD (NN).

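### Phase 1 ORR is planned only in the Efficacy Evaluable set, so treated subjects never scanned on study leave the denominator, and no all-treated ORR is planned beside it

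*Combined protocol and SAP*

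**What the plan says.** Section 10.1.2 sets four conditions for the EE set: at least one dose, central-laboratory confirmation of the local RET result, baseline measurable disease together with "at least 1 on-study tumor assessment per RECIST v1.1", and no major protocol violation that could affect efficacy. It then states: "The EE analysis set will be used for efficacy analyses for Phase 1".

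Section 10.1.1 defines the FAS as everyone given any full or partial dose, and lists its uses: "The FAS set will be used for the summary of subject dispositions, demographics, and baseline characteristics, and safety analysis". Efficacy is not among them.

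Section 10.3.4 says: "Radiologic assessments evaluated by the Investigator will be explored for Phase I in efficacy analysis set". Only one efficacy set is defined, so this is read as the EE set. The same section adds: "Number of subjects with ORR will be summarized".

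Section 10.3.4.1 defines ORR as the proportion with a confirmed complete or partial response, and requires confirmation: "A confirmed response is a response that persists on a repeat imaging performed at least 4 weeks after initial documentation of response". On the other side of the count, "Non-responders will include subjects without a confirmed objective response", and not-evaluable subjects are named in that group.

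**The concern.** The rule in Section 10.3.4.1 is conservative: a subject without a confirmed response, including one who is not evaluable, counts as a failure. Section 10.1.2 acts before that rule can. A treated subject with no on-study scan never enters the EE set, so is not counted at all.

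A missing scan is unlikely to be random. Early progression, death or toxicity before the first assessment are plausible causes, and all would be non-responses. Imaging in the current version follows standard of care (Section 7.7), and Sections 8.5 and 8.6 do not themselves state a scan at the end-of-treatment or safety follow-up visit.

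What is at stake is the efficacy percentage in the synoptic study report (Section 3) or in a publication (Section 14). Section 10.3.2 tabulates the number treated, but no section plans to show how many subjects each EE condition removes. A reader given only the EE percentage cannot tell how far it lies from the all-treated one, or on which side.

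**Working it through.** **Inputs from the documents.** 41 subjects enrolled across 9 dose levels (Section 10.2.1). This is an observed count, not a sample-size calculation, so there is no planned figure to reproduce. It is plausible for a 3+3 design: 3 to 6 subjects at each of 9 levels gives 27 to 54.

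**Assumptions.** All 41 were dosed and had measurable disease. The numbers of confirmed responders (r), unscanned subjects (k), subjects excluded for other reasons (m) and responders among those m (x) are not in the documents; the values below are illustrations. Section 10.3.5 plans pooling across cohorts for safety, but Sections 10.3.4 and 10.3.4.1 do not say whether ORR is pooled or shown by dose level, so both are worked.

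**Step 1: direction of the scan condition alone.** An unscanned subject cannot have a confirmed response, so r is unchanged and only the denominator falls:

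- all-treated ORR = r/41
- ORR after the scan condition = r/(41 − k)
- ratio = 41/(41 − k), which is at least 1 for any r > 0

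**Step 2: size if pooled, with r = 8 as an example.**

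| k | Denominator | Ratio | ORR |
|---|---|---|---|
| 0 | 41 | 1.00 | 8/41 = 19.5% |
| 2 | 39 | 1.05 | 8/39 = 20.5% |
| 6 | 35 | 1.17 | 8/35 = 22.9% |
| 10 | 31 | 1.32 | 8/31 = 25.8% |

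Exact 95% limits are 8.8% to 34.9% for 8/41 and 11.9% to 44.6% for 8/31. Even at k = 10 the shift of 6.3 percentage points is small beside the sampling uncertainty.

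**Step 3: size if shown by dose level.** The mean level size is 41/9 = 4.6. One unscanned subject in a level of n multiplies ORR by n/(n − 1): 6/5 = 1.20, 5/4 = 1.25, 4/3 = 1.33, 3/2 = 1.50. With one responder, a level of 6 goes from 16.7% to 20.0% and a level of 3 from 33.3% to 50.0%.

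**Step 4: net direction with all EE conditions.** Central RET confirmation and the major-violation condition can remove responders as well as non-responders:

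EE ORR = (r − x)/(41 − k − m)

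With r = 8, k = 2 and m = 4:

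- x = 0: 8/35 = 22.9%
- x = 1: 7/35 = 20.0%
- x = 2: 6/35 = 17.1%

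The all-treated figure is 19.5%. The two are equal at x = r(k + m)/41 = 8 × 6/41 = 1.17, so the EE figure falls below the all-treated one once 2 or more responders are excluded. The scan condition has a fixed direction; the EE set as a whole does not.

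**The case against.** The strongest case against concedes the text and disputes the consequence.

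- **A reader could rebuild the figure.** The scan condition leaves the responder count alone, that count is to be summarized, and the number treated is tabulated. For this condition alone, dividing one by the other gives the all-treated ORR. That stands only as far as it goes: the other EE conditions may have removed responders, and without exclusion counts the reader cannot know whether the division is valid.
- **The remedy changes more than the scan rule.** An FAS-based ORR also readmits subjects without central RET confirmation and those with major violations, so the contrast does not isolate the scan condition. This is fair, and is why exclusions must be listed by condition as well.
- **A separate SAP may cover it.** The opening of Section 10 allows a SAP to modify the plan. No separate SAP text is available here, so the finding applies to the plan as written.
- **Nothing depends on the result.** ORR is exploratory, with no hypothesis, target or decision rule; the primary endpoints are dose-limiting toxicities and MTD/RP2D; development has stopped. This stands, and limits the importance of the point.
- **The size is assumed, and k could be zero.** This also stands. In addition, the condition refers to imaging on study, not on treatment, so a scan after the last dose may qualify. Only subjects never imaged on study are lost.

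**Conclusion.** The concern holds. As written, Phase 1 ORR is planned only in a set that drops treated subjects never imaged on study, and no all-treated ORR accompanies it. By the plan's own definition of response, that condition taken alone can only raise the proportion or leave it unchanged.

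The size cannot be fixed from the documents. On the pooled assumptions above the factor is 1.05 to 1.32 for 2 to 10 unscanned subjects. By dose level, one unscanned subject gives 1.20 in a level of 6 and up to 1.50 in a level of 3. The net difference between EE and all-treated ORR could have either sign because of the other EE conditions. The responder count is unaffected by the scan condition, and the primary endpoints are not touched. This is a reporting gap that should be closed, not a threat to the study's main conclusions.

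**What to change.** In Sections 10.1.2 and 10.3.4, add ORR in all FAS subjects with measurable disease at baseline, reported beside the EE ORR. Count subjects with no on-study assessment as non-responders, in line with Section 10.3.4.1. Inclusion criterion 6 already requires measurable disease, so this denominator should be close to all treated subjects.

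Report the number excluded from the EE set by each condition. Showing how many of those excluded had a confirmed response would let a reader separate the scan condition from the others. An exact 95% confidence interval for each ORR is optional.

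The cost is wording in two sections, one table and one listing, with no new data. The added figure may be lower than the EE ORR or, because of the other EE conditions, higher.

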4. STUDY DESIGN

4.1. Overall Study Design

This is a Phase 1/2 multi-center, first-in-human (FIH), open-label study designed to evaluate the safety, tolerability, PK, and efficacy of the novel RET/SRC inhibitor TPX-0046 in adult subjects with advanced/metastatic solid tumors harboring oncogenic *RET* fusions or mutations. The global study consists of two portions as shown in Figure 2: 1) Phase 1 Dose Escalation, Food Effect Sub-study, and Dose Expansion in 6 cohorts, and 2) Phase 2 preliminary efficacy evaluation in six defined subject cohorts.

As the study enrollment will close prior to completing Phase 1 dose escalation, the Phase 1 food effect substudy, Phase 1 dose expansion, and Phase 2 activities will not take place.

Figure 2: Study Design

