7.6. Cardiac Safety Monitoring

7.7. Cardiac safety monitoring should be done based on symptomatology and at Investigator's discretion. Tumor Response Assessments

Tumor response assessments will be performed per standard of care.

Imaging studies will include a computerized tomography (CT) or magnetic resonance imaging (MRI) scan of the brain, chest, abdomen, pelvis. For subjects diagnosed with primary brain tumors, only the MRI of the brain will be required at Screening and during the study.

Tumor assessments will include all known or suspected disease sites and will be performed per specified timepoints according to the Schedules of Activities. For all tumor assessments, the method of assessment that was used at Screening should be the same method used throughout the study.

For all subjects, radiographic confirmation of objective tumor response or disease progression will be based on RECIST v1.1 and assessed locally.

Subjects discontinuing study treatment before documented radiographic progression will complete an EOT visit and safety follow-up visit per Section 8.4.

For subjects discontinuing the study treatment due to documented radiographic progression survival status will be obtained via a phone call or medical chart review, including information about subsequent anticancer therapies (including best response) every three months until death, loss of follow-up, or withdrawal of consent, whichever comes first.

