8.7. Subject Discontinuation and Withdrawal from Study

A subject may be discontinued from study treatment at any time if the subject, the Investigator, or the Sponsor Medical Monitor determine that it is not in the subject's best interest to continue on study. The following is a list of possible reasons for early discontinuation of study treatment:

- Disease progression (treatment beyond radiographic or clinical progression will not be allowed)
- Any adverse event that cannot be adequately managed with dose modifications, including dose interruption > 28 days (unless there is reasonable evidence of clinical benefit to justify continuation on the protocol which must be previously discussed with Turning Point Therapeutics)
- Protocol violation requiring discontinuation of study treatment
- Subject is not compliant with study procedures
- Lost to follow-up
- Subject withdrawal of consent for further treatment
- Investigator identifies alternative treatment option for the patient
- Turning Point Therapeutics' early termination of study. Reasons for terminating the study may include, but are not limited to, the following:

- All enrolled subjects have discontinued study treatment
- The incidence or severity of AEs in this or other studies indicates a potential health hazard to subjects
- Subject enrollment is unsatisfactory

Data to be collected for the EOT visit are described in the Schedules of Assessments.

Subjects will be followed for at least 28 calendar days after the last dose of TPX-0046. If a subject is discontinued from treatment due to an AE, the subject will be followed until the AE has resolved or stabilized as per Section 9.3.4.

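### Condition (4) of the only efficacy set lets on-treatment protocol violations remove subjects from the exploratory ORR, in an open-label study with no all-treated ORR beside it

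*Combined protocol and SAP*

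**What the plan says.** Section 10.1.2 sets four conditions for the EE set: at least one dose, central confirmation of the RET alteration, measurable disease at baseline with "at least 1 on-study tumor assessment per RECIST v1.1", and a requirement that subjects "have no major protocol violations that could affect efficacy". The section then states: "The EE analysis set will be used for efficacy analyses for Phase 1".

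No other set is assigned to efficacy. On the all-treated set, section 10.1.1 says: "The FAS set will be used for the summary of subject dispositions, demographics, and baseline characteristics, and safety analysis".

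On the reading of response, section 10.3.4 says: "Radiologic assessments evaluated by the Investigator will be explored for Phase I in efficacy analysis set". The text on tumor response assessments (7.7) adds that "radiographic confirmation of objective tumor response or disease progression will be based on RECIST v1.1 and assessed locally". Section 4.1 describes a "first-in-human (FIH), open-label study designed to evaluate the safety, tolerability, PK, and efficacy" of TPX-0046.

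Section 10.3.4.1 defines ORR as the proportion with confirmed CR or PR and counts not-evaluable subjects as non-responders. Section 8.7 lists, among possible reasons for stopping treatment, "Protocol violation requiring discontinuation of study treatment". Section 10 defers detailed methods to a separate SAP, whose text is not in the document supplied.

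**The concern.** Condition (4) carries no timing limit. The protocol sets several on-treatment rules whose breach could plausibly bear on efficacy: prohibited CYP-related drugs (6.5.1), other anti-tumor therapy (6.5.2), chronic corticosteroids (6.5.6) and dosing compliance (6.4, 7.4). Such breaches happen after treatment starts and may follow from toxicity or from a treatment that is not working. Excluding subjects for them makes the denominator depend on post-baseline events.

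The test is also a judgement. Section 10.1.2 does not define a major violation, name who decides, require the decision to be made without response data, or fix it before ORR is tabulated. With open-label treatment and local reading, nothing in the text keeps the classification separate from the outcome.

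At stake is whether the ORR in the synoptic report describes the subjects treated or a subset chosen partly on what happened to them.

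**Working it through.** **Step 1: can an on-treatment violation lead to exclusion?** Condition (4) refers to major violations that could affect efficacy and says nothing about when they occur. Section 8.7 shows that violations during treatment are foreseen, although it is not linked to the EE set. Eligibility breaches and on-treatment breaches both fall within the wording.

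**Step 2: can response be visible when condition (4) is applied?** Condition (3) needs an on-study scan. For any subject whose inclusion turns on condition (4) alone, some locally read response data therefore exist by the time all four conditions can be applied. The text does not say when violations are classified or who does it, so visibility is permitted, not shown.

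**Step 3: does another planned analysis offset this?** Sections 10.3.4 and 10.3.4.1 plan no ORR in the FAS and no sensitivity analysis. The disposition table in 10.3.2 does not include exclusions from the EE set.

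**Step 4: size.** The plan has no figure to reproduce: it states no target ORR and no efficacy sample-size calculation. The one input from the plan is 41 subjects enrolled across 9 dose levels (10.2.1). The responder count *r* and the number excluded *k* are assumptions. Using N = 41 further assumes that every enrolled subject was dosed and meets the other three conditions.

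- Before exclusion: ORR = *r*/N.
- Excluding *k* non-responders: *r*/(N − *k*), a rise of *rk*/[N(N − *k*)].
- Excluding *k* responders: (*r* − *k*)/(N − *k*), a fall of (N − *r*)*k*/[N(N − *k*)].

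For *r* = 8, the starting value is 8/41 = 19.5% (exact 95% CI 8.8% to 34.9%).

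- 2, 4 or 8 non-responders excluded: 8/39 = 20.5%, 8/37 = 21.6%, 8/33 = 24.2%. The last is a rise of 64/(41 × 33) = 4.7 points.
- 1 or 2 responders excluded: 7/40 = 17.5%, 6/39 = 15.4%.

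Over a range of assumed responder counts:

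| Assumed *r* of 41 | No exclusion (exact 95% CI) | 2 non-resp. out | 4 non-resp. out | 6 non-resp. out | 1 resp. out | 2 resp. out |
|---|---|---|---|---|---|---|
| 4 | 9.8% (2.7–23.1) | 10.3% | 10.8% | 11.4% | 7.5% | 5.1% |
| 8 | 19.5% (8.8–34.9) | 20.5% | 21.6% | 22.9% | 17.5% | 15.4% |
| 12 | 29.3% (16.1–45.5) | 30.8% | 32.4% | 34.3% | 27.5% | 25.6% |
| 16 | 39.0% (24.2–55.5) | 41.0% | 43.2% | 45.7% | 37.5% | 35.9% |

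For *r* from 4 to 16 and 1 to 6 non-responders excluded, the rise is 0.2 to 6.7 points. For the same *k*, excluding responders moves the rate (N − *r*)/*r* times as far as excluding non-responders; at *r* = 8 this is 33/8, about 4 times.

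**The case against.** The strongest reply is that the point rests on silence. The condition does not mention on-treatment events, a sponsor decision or timing, and the separate SAP may hold the violation list and the classification procedure. This stands in part. The documents do not show that anyone will classify violations with responses in hand, and a reader who infers that goes beyond the text. What remains is that the rule as written admits such exclusions, and nothing in the document supplied prevents them.

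Second, the result matters little. The stated endpoints are DLTs and MTD/RP2D, efficacy is only explored, enrollment is closed and later stages will not take place. The assumed shifts also lie inside the confidence interval. This stands as a limit on weight. It does not remove the point, because the interval reflects sampling error and not selection of the denominator.

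Third, a reader might infer that the effect of exclusions could never be detected. That is too strong. Section 10.3.4 plans a count of responders and 10.3.2 a count of treated subjects. If only non-responders were excluded, dividing one by the other recovers the all-treated rate. An excluded responder, however, would not show in those counts.

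Fourth, changing condition (4) alone would not be enough, since condition (3) still drops anyone who stops before a first scan. This is correct, and the fix takes account of it.

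**Conclusion.** The point holds at modest weight. The only set assigned to Phase 1 efficacy has an exclusion rule that can act on post-baseline violations, by judgement, in an open-label study with local reads, and no all-treated ORR is planned beside it. With an assumed 8 of 41 responders, the ORR could move from 19.5% up to 24.2% (8 non-responders excluded) or down to 15.4% (2 responders excluded). These figures depend on assumed counts and show that the ORR can move, not that it did or in which direction.

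Three stronger readings are not supported:

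- **That the decision to stop development rests on this ORR.** Section 3 attributes the decision to the whole of the clinical information and dates its communication to 03 October 2022. It mentions neither ORR nor the EE set, and 10.1.2 still describes the EE analysis as to come.
- **That large swings at a single dose level are at issue.** One exclusion among four or five subjects would move a rate sharply, but 10.3.4 does not plan ORR by dose level.
- **That condition (4) is aimed at on-treatment violations.** It covers eligibility breaches as well; the fault is the missing limit.

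**What to change.** **Main change.** In 10.1.2 and 10.3.4, make the ORR analysis the one in all treated subjects with measurable disease at baseline, with subjects who have no post-baseline scan counted as non-responders. This agrees with 10.3.4.1, which already treats not-evaluable subjects as non-responders. It also removes the loss of early stoppers through condition (3).

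**If the EE set is kept**, label it supportive and:

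- limit condition (4) to eligibility violations that existed before the first dose;
- have them classified from the deviation log without response data, and fix the list before ORR is tabulated;
- list every excluded subject, and every on-treatment major violation, with the reason and best response.

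**Cost.** A few sentences of text, one extra summary and one listing. No new data are needed. The reported ORR may be slightly lower because non-responders who would have been excluded stay in.
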